7.7.5. AC composite improvement from baseline

• Computation of the Endpoint

The first AC composite improvement endpoint is defined as the occurrence of either or both of the following conditions for a given subject's ear for a given visit: 1) AC improvement ≥ 10 dB HL from baseline for two contiguous frequencies as described in Section 7.7.3 or 2) AC improvement ≥ 15 dB HL from baseline for any frequency as defined in Section 7.7.4.

The second AC composite improvement endpoint is defined as the occurrence of either or both of the following conditions for a given subject's ear for a given visit: 1) AC improvement \geq 15 dB HL from baseline for two contiguous frequencies as described in Section 7.7.3 or 2) AC improvement \geq 20 dB HL from baseline for any frequency as defined in Section 7.7.4.

• Analysis of the Endpoint

The incidence of each AC composite improvement endpoint at each post-baseline visit for treated ears will be summarized using frequencies and percentages for treated ears by visit and treatment group for subjects in the FAS.

In treated ears only for subjects in the FAS, post-baseline treatment group comparisons through day 90 for incidence of AC composite improvement from baseline may be analyzed using a GEE model. With the binomial distribution assumption and logit link, the model will include fixed effects of treatment group, visit, interaction between visit and treatment group, baseline mean dB HL threshold (AC over 9-16 kHz), interaction between baseline mean dB HL threshold (AC over 9-16 kHz) and visit, and randomization stratification factors. If the model fails to converge, the randomization stratification factors will be excluded from the model. The odds ratios along with 95% CIs and p-values between treatment groups will be reported by post-baseline visit.

7.7.6. Shift from baseline of no signal to any signal by frequency

• Computation of the Endpoint

For each frequency, shifts from no signal to any signal will be computed in subjects in the FAS with no signal (missing/imputed hearing response) at baseline in the treated ear. At each post-baseline visit, subjects with any signal (any non-missing/not imputed hearing response) in the treated ear will be flagged as 1 and as 0, otherwise. The endpoint will utilize imputed values per Section 7.7.

• Analysis of the Endpoint

For each frequency, the incidence of shifts from no signal at baseline to any signal at each post-baseline visit for treated ears will be summarized using frequencies and percentages by visit and treatment group for subjects with no signal at baseline in the FAS.

7.7.7. Shift from baseline of no signal to any signal in two contiguous frequencies

• Computation of the Endpoint

Shifts from no signal in two contiguous frequencies at baseline to any signal in two contiguous frequencies at each post-baseline visit will be computed in subjects in the FAS with no signal (missing/imputed hearing response) at baseline in the treated ear for any two contiguous frequencies. At each post-baseline visit, subjects with any signal (any non-missing/not imputed hearing response) in the treated ear at the same two contiguous frequencies will be flagged as 1 and as 0, otherwise. The endpoint will utilize imputed values per Section 7.7.

• Analysis of the Endpoint

The incidence of shifts from no signal in two contiguous frequencies at baseline to any signal in two contiguous frequencies at each post-baseline visit for treated ears will be summarized using frequencies and percentages by visit and treatment group for subjects in the FAS with no signal in any two contiguous frequencies at baseline in the treated ear.

7.7.8. Shift from baseline of no signal to any signal in three contiguous frequencies

• Computation of the Endpoint

Shifts from no signal in three contiguous frequencies at baseline to any signal in three contiguous frequencies at each post-baseline visit will be computed in subjects in the FAS with no signal (missing/imputed hearing response) at baseline in the treated ear for any three contiguous frequencies. At each post-baseline visit, subjects with any signal (any non-missing/not imputed hearing response) in the treated ear in the same three contiguous frequencies will be flagged as 1 and as 0, otherwise. The endpoint will utilize imputed values per Section 7.7.

• Analysis of the Endpoint

The incidence of shifts from no signal in three contiguous frequencies at baseline to any signal in three contiguous frequencies at each post-baseline visit for treated ears will be summarized using frequencies and percentages by visit and treatment group for subjects in the FAS with no signal in three contiguous frequencies at baseline in the treated ear.

7.8. Examination of Subgroups

Non-stratified treatment differences between treatment groups in the incidence of WR Improvement at Day 90, as defined in section 7.3.1, for WR in Quiet improvement (Maryland CNC) in the FAS will be summarized within the subgroups listed below along with 95% CIs in a forest plot. Missing data will be imputed using LOCF. In the case a subgroup includes less than 20 subjects, the analysis for the given subgroup will not be carried out or combining subgroups may be considered.

• Subject Demographics

- o Sex
- o Race
- Ethnicity
- Age (18 to <35, 35 to <50, 50 to 65)
- Baseline Disease Characteristics
 - Duration of hearing loss (≤ 1 , >1 to 5, >5 to 10, >10 years from screening)
 - Etiology of hearing loss
 - Individual randomization stratification factors:
 - Visit 2 (Day -15) Maryland CNC Word Recognition Score (above or equal to 28% words in quiet correct, below 28% words in quiet correct)
 - Hearing loss laterality (unilateral, bilateral)

8. SAFETY EVALUATION

8.1. Overview of Safety Analysis Methods

The assessment of safety of single dose of FX-322 or Placebo in subjects with acquired sensorineural hearing loss is an objective of this study. The safety analyses will be performed for the SfAS and will include treatment-emergent adverse events (TEAEs), serious adverse events (SAEs), vital signs, physical examination, otoscopic examination, tympanometry, concomitant medications, and C-SSRS assessments. Tabular summaries of descriptive statistics will be presented for all subjects included in the SfAS and subjects will be classified into actual treatment groups. Where appropriate, the actual treated ear will be distinguished from the actual untreated ear.

Safety data will generally not be imputed, except for partial and missing dates, which will be imputed only for defining TEAEs and concomitant medications for analysis and reporting purposes. The detailed imputation rules are specified in section 8.3.1. Imputed dates will not be presented in data listings.

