**Statistical Analysis:**

**Sample Size:** The sample size of 112 evaluable subjects, in a 1:1 allocation ratio of FX-322 and Placebo provides 80% to show improvements in WR.

**Statistical Methods:** Descriptive summaries will be provided for patient disposition, demographic and baseline disease data by treatment group.

Efficacy analysis of continuous endpoints will be examined via a Mixed Model for Repeated Measures (MMRM). Inferential analyses for categorical endpoints will be analysed using univariate methods and/or Generalized Estimating Equations (GEEs) (or appropriate longitudinal methods as detailed in the SAP). When appropriate, models will include adjustments for baseline as well as the stratification factors used at randomization and clinically relevant confounders as identified in the SAP. Departures of these models from the statistical assumptions will be assessed and alternative approaches may be employed.

Summary statistics for efficacy endpoints will be provided by treatment group over the study and at specific timepoints. Comparisons between FX-322 and placebo and 95% confidence interval of the difference will also be calculated.

The incidence of treatment-emergent adverse events will be presented by preferred term and body system using the Medical Dictionary for Regulatory Activities (MedDRA®). Tabulations will be provided by seriousness, severity, and relationship to study drug. Audiology, tympanometry and otologic data will be presented as summary statistics at each timepoint as well as changes from baseline and/or shift tables. All subjects exposed to study drug will be included in the Safety Analysis Set and included in the safety analyses according to the actual treatment group regardless of the randomized assignment.

Details of all planned statistical analyses and methods will be provided in the SAP, and will be finalized prior to study blind break for the primary analysis.

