## 8.2 Known Potential Risks

The risks of intratympanic injection of FX-322 have been carefully studied in nonclinical toxicology studies, as well as in a number of clinical trials. Based on these studies, the risks appear to be similar to those experienced with intratympanic injections of other materials, such as steroids, that are not FDA-approved. The risks of single intratympanic injections are characterized as persistent eardrum perforation, pain or bleeding with injection, temporary dizziness, middle ear infection, and conductive or sensorineural hearing loss. A published clinical trial using multiple intratympanic injections of a steroid in SSNHL patients has shown the majority of adverse events to be associated with the injection procedure, with eardrum perforations reported at less than 4% (Rauch et al., 2011; McLean et al., 2021).

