## **14 ADVERSE EVENTS**

### **Adverse Event Definition**

An AE is defined as any untoward medical occurrence in a clinical study subject administered a medicinal product which does not necessarily have a causal relationship with this treatment. An AE can therefore be any unfavorable and unintended sign (including an abnormal laboratory finding), symptom, or disease temporally associated with the use of a medicinal (investigational) product, whether or not it is related to the medicinal (investigational) product. This includes an exacerbation of pre-existing conditions or events, intercurrent illnesses, drug interaction or the significant worsening of the indication under investigation that is not recorded elsewhere on the CRF under specific assessments. Anticipated fluctuations of pre-existing conditions, including the disease under study that do not represent a clinically significant exacerbation or worsening need not be considered AEs.

It is the responsibility of the investigator to document all AEs that occur during the study. AEs will be elicited by asking the subject a nonleading question, for example, "Have you experienced any new or changed symptoms since we last asked/since your last visit?". AEs will be recorded from the time of study treatment (Visit 3) through the end of the observational period, or final study visit. AEs should be reported on the appropriate page of the CRF.

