## **Adverse Events of Special Interest (Audiometric and Otoscope)**

If any of the following criteria are met through Visit 6 (Day 90), the event will be recorded as an adverse event of special interest (AESI) per ASHA guidelines (ASHA 1994):

- Asymmetric loss of hearing greater than or equal to 20 dB at any one frequency in the treated ear compared to Visit 3.
- Asymmetric loss of hearing greater than or equal to 10 dB at two adjacent frequencies in the treated ear compared to Visit 3.
- Asymmetric loss of response at three consecutive test frequencies where responses were previously obtained in the treated ear compared to Visit 3.

For word recognition testing, a follow up visit score through Visit 6 (Day 90) in the treated ear that falls below the lower limit of the 95% confidence interval of the Visit 3 word recognition score will be considered an AESI (Carney and Schlauch, 2007).

Additionally, if the subject experiences a perforation greater than 25% of the tympanic membrane in the treated ear through Visit 6 (Day 90) this will be recorded as an AESI.

If any subjects in the study experience the same AESI through Visit 6 (Day 90), the Medical Monitor will discuss these with the Principal Investigators and each subject's condition will be discussed.

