administration of study drug and the year is the same as the year of the date of administration of study drug, and 2) the end date is on or after the date of administration of study drug or the end date is completely missing, in which case the start day and month will be set to that of the date of administration of study drug.

- For a missing end day where the month and year are present, the end day will be set to the last day of the month, unless the month and year are the same as the month and year of the last contact date for the subject, in which case the end day will be set to that of the subject's last contact date, which is captured in SDTM as DM.RFPENDTC (Date/Time of End of Participation) with derivation rule specified in the study SDTM specifications.
- For a missing end day and month where the year is present, the end day and month will be set to the subject's last contact date, unless the year of the subject's last contact date is greater than the end year, in which case the end day and month will be set to December 31st.

Completely missing dates will be imputed for the purposes of classifying TEAEs as follows:

- For an entirely missing start date (i.e., day, month, and year are missing), the start date will be set to the date of administration of study drug unless the end date is prior to the date of administration of study drug, in which case the start date will be set to the end date.
- 8.4. Deaths, Serious Adverse Events, and Other Significant Adverse Events

Treatment-emergent SAEs, TEAEs leading to study withdrawal, and fatal TEAEs will be summarized for all subjects in the SfAS by treatment group for the following:

- Overall summary of SAE by SOC and PT
- Overall summary of TEAE leading to study withdrawal by SOC and PT
- Overall summary of fatal TEAE by SOC and PT

SAEs, adverse events leading to study withdrawal, and fatal AEs will be presented in data listings for subjects in the SfAS.

Adverse Events of Special Interest (AESI), defined in the Protocol, will be summarized by treatment group, SOC, and PT for all subjects in the SfAS. AESIs that occur after study treatment injection will be presented in a data listing for subjects in the SfAS.

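### Hearing loss after dosing is counted in the safety section only from events that sites record, and no decibel or word-recognition criterion applies at Days 180 and 270

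*SAP*

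**What the plan says.** Protocol 8.2 names "conductive or sensorineural hearing loss" among the risks of the injection. The synopsis, in the paragraph on adverse events and the Safety Analysis Set (SfAS), states: "Audiology, tympanometry and otologic data will be presented as summary statistics at each timepoint as well as changes from baseline and/or shift tables". SAP 8.1 lists, after adverse events, "vital signs, physical examination, otoscopic examination, tympanometry, concomitant medications, and C-SSRS assessments". SAP Section 11 declares no changes from the protocol's analyses.

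Protocol Section 14 defines AESIs for the treated ear against Visit 3:
- loss of at least 20 dB at one frequency ("Asymmetric loss of hearing greater than or equal to 20 dB at any one frequency in the treated ear compared to Visit 3");
- loss of at least 10 dB at two adjacent frequencies;
- lost response at three consecutive frequencies;
- a word-recognition score below the lower 95% limit;
- a large tympanic membrane perforation.

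The window is fixed: "If any of the following criteria are met through Visit 6 (Day 90), the event will be recorded" as an AESI. SAP 8.4 says that AESIs, "defined in the Protocol, will be summarized by treatment group, SOC, and PT for all subjects in the SfAS". SAP 8.3 also tabulates ear-related treatment-emergent events by ear and by phase, with a phase after Day 90.

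The adverse event definition in Protocol Section 14 includes "significant worsening of the indication under investigation that is not recorded elsewhere on the CRF under specific assessments". Protocol 11.1 makes every new clinically relevant finding after randomisation an adverse event.

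**The concern.** The drug is injected to improve hearing, and loss of hearing is a stated risk. Safety is the only secondary objective. A reader of the study report will want the proportion of ears that got worse in each arm beside the proportion that improved.

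As planned, the safety comparison depends on each site comparing each audiogram with Visit 3, recognising that a criterion is met, and entering an event. The audiograms are in the database, so one rule could be applied to every ear. After Day 90 no criterion applies, although Protocol 12.7 and 12.8 schedule full audiometry and word recognition at Days 180 and 270. For that period the count rests on ear-related adverse events, and the two protocol rules on whether a worse audiogram is an adverse event point in different directions.

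**Working it through.** The plan gives no figure on this point to reproduce. The check traces each planned analysis that could count a worsened ear, then tests how sensitive the nearest substitute is.

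**1. Coverage of the AESI criteria.** Post-dose audiology visits are Days 30, 60, 90, 180 and 270 (Protocol Table 2). The criteria cover 3 of 5 visits and 90 of 270 days (90/270 = 33%).

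**2. Flags derived from audiometry.** The threshold responder flags are 4 in SAP 7.6.3, 4 in 7.6.4, 4 in 7.6.5, and 2 each in 7.7.3, 7.7.4 and 7.7.5: 4+4+4+2+2+2 = 18. All are labelled as improvement. The extended-high-frequency shifts (7.7.6 to 7.7.8) run only from no signal to any signal. All use the Full Analysis Set (FAS) by randomised arm.

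**3. Sign of those flags.** SAP 7.6.3, 7.6.4, 7.7.3 and 7.7.4 compute post-baseline minus baseline and require a positive cut-off. Thresholds rise as hearing worsens. A change from 60 to 50 dB (better) gives 50 − 60 = −10, flag 0. A change from 60 to 70 dB (worse) gives 70 − 60 = +10, flag 1. This is a separate error. Correcting it leaves no worsening count, and a new program must not copy it.

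**4. The PTA category shift (SAP 7.6.7).** This table runs in both directions at every visit, so it is the nearest substitute. PTA is the mean of 0.5, 1, 2 and 4 kHz, in categories <26, 26-40, 41-55, 56-70 and >70.
- A 20 dB loss at one of the four frequencies moves PTA by 20/4 = 5 dB.
- A 10 dB loss at two of the four moves it by (10+10)/4 = 5 dB.
- Loss confined to 6-16 kHz moves it by 0 dB.

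For each integer baseline PTA from 35 to 85 dB (the eligible range at Screening; 51 values, equal weights assumed), the number that change category is:

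| PTA worsening | Baselines changing category |
|---|---|
| 5 dB | 15 of 51 |
| 10 dB | 26 of 51 |
| 15 dB | 36 of 51 |
| 20 dB | 36 of 51 |

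For 5 dB these are 36-40, 51-55 and 66-70. The 15 values above 70 can never move to a worse category.

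**5. Background from chance.** Take one 50-word list at Visit 3 and three independent 50-word follow-ups, with no true change, true scores of 10-60%, and the n = 50 lower limits in SAP 14.2. A score falls below the limit in 2.7-3.0% of ears per visit, and at least once in three visits in 6.6-7.7%. For 124 treated ears that is 0.066 × 124 = 8.2 to 0.077 × 124 = 9.5.

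**6. Other gaps.** Protocol 15.6.1 promises AESI summaries by treated and non-treated ear. SAP 8.4 tabulates by treatment group, system organ class and preferred term, without that split and without separating the criteria.

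**The case against.** The plan has more than SAP 8.1 shows. The AESI table in 8.4 does count worsened treated ears through Day 90, by arm, in the SfAS. Up to then the adverse event definition cannot remove a case, because the protocol requires qualifying events to be recorded. Ear-related events after Day 90 have their own phase in SAP 8.3. Section 7 also plans per-frequency thresholds by visit for both ears (including 9-16 kHz), an air-bone imbalance shift at each frequency that would show a new conductive gap, and word-recognition scatterplots with the critical limits at each visit. All of this stands. It rules out the stronger reading that no safety analysis counts worsening, or that late loss cannot appear anywhere. It does not supply a count of ears by a decibel or word-recognition criterion at Days 180 and 270.

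The protocol classes audiometry as an efficacy measure, and its safety endpoints omit it. Against that, the synopsis safety paragraph names audiology, and Protocol 10.2 includes it in safety monitoring. FAS and SfAS differ only for wrong-ear or wrong-treatment dosing, so the choice of set matters little in practice.

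The decibel criteria require asymmetric loss without saying how that is measured. This stands, and the fix must deal with it. The Day 90 limit was a deliberate amendment, so the reporting window is not challenged here.

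Finally, the chance rate applies to both arms and would also fill the proposed table. It is not evidence that sites under-report, and sites are blinded to treatment.

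**Conclusion.** The point holds as a gap in the safety analysis. Through Day 90, worsening is counted only as sites record it. At Days 180 and 270, two of the five post-dose audiology visits, no decibel or word-recognition criterion is applied. The SAP safety section leaves out the audiology summaries named in the synopsis and the ear split in Protocol 15.6.1. Two protocol passages disagree on whether worsening already captured on the audiometry form is an adverse event.

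The PTA shift table does not close the gap: 15 of 51 baselines change category for a 5 dB shift, assuming equal weights over 35-85 dB, and none for loss confined to 6-16 kHz.

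A reader might infer that hearing harm goes uncounted, or that the 6.6-7.7% chance rate measures missed events. The documents support neither. Nothing here changes the primary analysis, sample size or power. This is a cheap improvement.

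**What to change.** Add to SAP Section 8 a descriptive table on the SfAS, by actual treatment, for treated and untreated ears separately, at each post-dose visit through Day 270. Give n (%) of ears meeting the protocol's existing decibel, loss-of-response and word-recognition criteria against Visit 3, derived by program, beside the site-reported AESI table.

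- Apply the decibel criteria to each ear on its own, and state how asymmetry is programmed. One option is a further row for treated ears that meet a criterion when the untreated ear does not.
- State whether the word-recognition criterion uses Maryland CNC, W-22 or both. Both are tested at every visit and the AESI text does not say.
- Code loss as an increase in threshold.
- Restore the treated versus non-treated split for AESIs in SAP 8.4.
- Reconcile the adverse event definition in Protocol Section 14 with Protocol 11.1. The AESI reporting window can stay as it is.

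The cost is SAP wording, one program and one table; sites do nothing new. The downside is a background of chance events in both arms, about 7% of ears for word recognition over three visits under the assumptions above, and more when later visits are added. The table should be read as a comparison between arms, not as a rate of harm.

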8.2. Extent of Exposure

Exposure will be summarized descriptively by actual treatment group and overall for subjects in the SfAS for the following parameters:

- Number and percentage of subjects receiving study treatment in the study ear
- Number and percentage of subjects with a full dose administered
- Number and percentage of subjects receiving incorrect study treatment in the study ear to be treated
- Number and percentage of subjects treated in the non-study ear

An exposure listing will be provided, including all available exposure data.

